RATIONALE	Mucus plugging of the airway is consistently found in fatal and near-fatal asthma. The role of mucus as a cause of airflow obstruction in acute severe asthma suggests that mucus plays a role in the pathophysiology of airflow obstruction in chronic severe asthma as well. This role has been hard to prove, however, in large part because of difficulty in showing that mucus occludes the lumen in chronic severe disease. Using a novel approach of scoring mucus occlusion, we have used CT imaging to uncover that a majority of asthmatics in the NHLBI Severe Asthma Research Program (SARP) have at least one lung segment with a mucus plug and 27% have more than four lung segments with mucus plugs. Historically, studies of mucolytics, like n-acetylcystine (NAC), have not shown benefit in other obstructive lung diseases, like COPD. However, utilizing CT mucus scores as a biomarker, we believe that mucolytic treatment may prove useful for those with significant mucus impaction.	
STUDY DESIGN	This is a randomized, double-blind, placebo-controlled phase 4 study.	
PRIMARY OBJECTIVE	The primary objective is to assess the clinical efficacy as measured by the change in pulmonary function over the seven day treatment period.	
SECONDARY OBJECTIVES	The secondary objectives are to assess the clinical efficacy as measured in a subgroup of participants by the change in CT mucus score from baseline to end of treatment, and identify characteristics of those participants who benefit from mucolytic treatment.	
NUMBER OF PARTICIPANTS	30	
PARTICIPANT SELECTION CRITERIA	 Inclusion Criteria: Male or female between the ages of 18 and 70 years of age at Visit 0. Able to perform reproducible spirometry according to ATS criteria Clinical history consistent with moderate to severe asthma for 1 year or greater. 	

Version #:1.5 Version Date: 8/5/2016 Page 7 of 41

	4. Post-bronchodilator FEV1 <90% of predicted		
	5. Prescription and daily use of inhaled corticosteroid (ICS) equivalent to 80mcg of beclomethasone or greater		
	6. CT mucus score >3 (determined during the initial screening process, provided the prior two conditions are met)		
	7. Written informed consent obtained from participant and ability for participant to comply with the requirements of the study.		
	Exclusion Criteria:		
	1. Pregnant, breastfeeding, or unwilling to practice birth control during participation in the study.		
	2. Presence of a condition or abnormality that in the opinion of the Investigator would compromise the safety of the patient or the quality of the data.		
	3. History of intolerance to study medications.		
	4. Current use of carbamazepine		
	5. Angina which includes a treatment plan with PRN nitroglycerin or nitrites		
	6. Smoking of tobacco or other recreational inhalants in last year and/or >10 pack-year smoking history		
	7. Current participation in an investigational drug trial		
	8. Other chronic pulmonary disorders, including (but not limited to) cystic fibrosis, chronic obstructive pulmonary disease, chronic bronchitis, vocal cord dysfunction (that is the sole cause of respiratory symptoms and at the PI's discretion), severe scoliosis or chest wall deformities that affect lung function, or congenital disorders of the lungs or airways.		
TEST PRODUCT,	20% NAC (5)		
DOSE, AND ROUTE OF ADMINISTRATION	Product will be administered every 6-8 hours (3 times per day) for 7 days. Medication will be administered via a portable tabletop nebulizer.		
CONTROL	0.9% saline (5mL)		
PRODUCT, DOSE AND ROUTE OF ADMINISTRATION	Product will be administered every 6-8 hours (3 times per day) for 7 days. Medication will be administered via a portable tabletop nebulizer.		
DURATION OF	Participants will be enrolled in the study up to 132 days:		
PARTICIPATION	Screening: up to 90 days		
AND DURATION OF STUDY	Treatment Period 1: 7 days		
STUDY	Washout: 28 days		
	Treatment Period 2: 7 days		

Version #:1.5 Version Date: 8/5/2016 Page 8 of 41

	The total duration of the study is expected to be 24 months. Participant recruitment will happen on a rolling basis.	
CONCOMMITANT MEDICATIONS	Prohibited: Thiols and thiol derivatives Carbamazepine Nitroglycern and nitrates	
EFFICACY EVALUATIONS		
PRIMARY ENDPOINT	• The primary outcome is the % change in FEV1 from the start to the end of the treatment period (either placebo or 20% NAC).	
SECONDARY ENDPOINTS	Our secondary analysis is to determine the characteristics of participants that respond to NAC.	
OTHER EVALUATIONS	Rheological properties of sputum.	
SAFETY EVALUATIONS	Incidence of adverse events	
PLANNED INTERIM ANALYSES	When approximately 50% of patients have completed the study through Visit 6, an interim analysis for safety will be conducted by the UCSF Airway Clinical Research Study Quality Assurance Committee. Serious adverse events will be monitored by the committee on an ongoing basis throughout the study.	
STATISTICS Primary Analysis Plan	The primary outcome is the % change in FEV1 from the start to the end of the treatment period (either placebo or 20% NAC). The first analysis will be to test the assumption of negligible carryover effects from study period 1 to period 2. We will compare the sum of the outcome values measured in the two periods for each participant across the 2 sequence groups (placebo-20% vs. 20%-placebo) using an unpaired t-test. After no or negligible carryover effect has been confirmed, we will test for the difference in treatment effects between placebo and 20% NAC using a paired t-test.	
Rationale for Number of Participants	We propose a sample size of 30, which will provide us with the power to examine the effect of NAC in a subgroup of individuals with asthma who have CT evidence of intraluminal mucus and to identify the CT mucus score that performs best as a biomarker of treatment response to NAC. Participants will be enrolled if their CT mucus scores are >3.0. To calculate sample size for the one-week treatment period study, we used FEV1 measures from 219 adults with asthma published in Corren et al. NEJM, 2011¹. The authors found that the standard deviation for the change in FEV1 in liters from day 1 to day 7 was 19%. Using a standard deviation of 19 and a two-sided alpha of 0.05, we calculate a sample size of 30 to have 80% power to detect a	

Version #:1.5 Version Date: 8/5/2016 Page 9 of 41

change in FEV1 of 10% (a reasonable effect size because early studies of Pulmozyme in CF reported a 10% increase in FEV1 at day 3 of treatment).
1

Version #:1.5 Version Date: 8/5/2016 Page 10 of 41

1 BACKGROUND

Mucus plugging of the airway is consistently found in fatal asthma². Decades ago, Dunnill provided graphic descriptions in 20 cases of fatal asthma³ noting that "the cut surface of the lung showed a striking picture with numerous grey, glistening, mucous plugs scattered throughout the airway passages." He summarized that "pathologically, the outstanding feature of the asthmatic lung lies in the failure of clearance of the bronchial secretions." Others have confirmed these findings, and it is only a small minority of asthma deaths that are not associated with airway mucus impaction.

In non-fatal or near-fatal asthma exacerbations segmental collapse of lung lobes due to luminal occlusion is common. Lavage of these cases yields abnormal mucus plugs in the form of airway casts⁴. The combination of airway narrowing from concentric smooth muscle contraction with luminal obstruction by mucus marks asthma as uniquely dangerous among airway diseases in its propensity for sudden and sometimes fatal exacerbations. The role of mucus as a cause of airflow obstruction in acute severe asthma suggests that mucus plays a role in the pathophysiology of airflow obstruction in chronic severe asthma as well. This role has been hard to prove, however, in large part because of difficulty in showing that mucus occludes the lumen in chronic severe disease. Lungs are available at autopsy to show mucus occlusion in fatal asthma, and it is notable that there is

[figure not shown]

Figure 1: Intraluminal mucus in CT lung images of asthmatics. Mucus plugs in CT scan images (white arrows) were defined as complete occlusion of an airway lumen by mucus and were identified as tubular structures in longitudinal section with branching (A & B) or without branching (C) or as rounded opacities in cross-section (D). The latter were traced cephalad or caudad on adjacent slices to confirm their continuity with unocculded bronchi (red arrow).

evidence of occlusion in asthmatics who die with asthma (rather than because of it)⁵. But the field has yet to be persuaded of a role for mucus in airway dysfunction in chronic asthma.

1.1 Overview of Clinical Studies

Against this background, the preliminary data we show in Figs 1 and 2 are very important, because we show how CT lung images can reveal mucus plugs in chronic severe asthma and how these plugs are associated with lower lung function. Specifically, we use CT imaging to uncover that a majority (58%) of asthmatics in the NHLBI Severe Asthma Research Program (SARP) have at least one lung segment with a mucus plug and 27% have more than four lung segments with mucus plugs. Notably, asthmatics with a high mucus scores achieve a post albuterol FEV1 > 80% much less frequently than asthmatics who have a zero mucus score (Fig 3).

Examined another way, we find that all asthmatics with an FEV1 \leq 60% after

[figure not shown]

Figure 2. A. The CT mucus segment score is usually 0 in health but many asthmatics enrolled in the NHLBI Severe Asthma Research Program have scores above 0 with some as high as 15-19. B. The frequency distribution of mucus score in asthma shows that 42% of patients have a score of 0 (zero mucus score); among the remaining 58% of asthmatics, the median mucus score was 3.5, and we classified score between 0.5 and 3.5 as "low" and above 4.0 as "high".

albuterol treatment have abnormal mucus scores, whereas the majority of asthmatics with an FEV1 >80% with albuterol treatment have zero or low mucus scores (Fig 3). These data clearly implicate mucus plugs in the pathogenesis of airflow obstruction in asthma. One reason why this role for mucus plugging has been underappreciated in chronic severe asthma is that mucus-related symptoms are both insensitive and non-specific indicators of mucus. This is well illustrated in the table, which presents data for the prevalence of mucus-related symptoms in asthmatics with different mucus score categories. None of the mucus-related symptoms were significantly different in the zero, low or high mucus subgroups, and it is clear that these symptoms have very limited utility to investigate the

role of mucus in asthma or to identify asthmatics who might benefit from mucus-directed treatments.

1.2 Overview of Non-Clinical Studies

To test the hypothesis that airway mucus in asthma has abnormal elasticity, we performed rheology on induced sputum from 40 asthmatic participants recruited to UCSF as part of the SARP. The majority of these asthmatic participants (65%) had severe asthma. We compared the elastic modulus (G') of these participants to induced sputum G' in 11 healthy controls. We found that the G' in the asthmatic group was significantly higher than normal (Fig 4A). Notably, we found a strong inverse correlation between G' and FEV1 % (Fig 4B). This finding suggests that stiff mucus in the airway of asthmatics could be a mechanism of mucus

[figure not shown]

Figure 3. Mucus scores in asthmatics with different FEV1 values (post 6-8 puffs of albuterol). Note that all asthmatics with an FEV1 <60% have abnormal mucus scores.

impaction of airways and airflow obstruction. It further suggests that decreasing mucus G' could be a treatment strategy to improve airflow. To determine if the G' of asthmatic sputum is a result of excessive mucin disulfide bridges (as it is in CF), we measured the G' in a subgroup of 6 asthmatics before and after the addition of n-Acetylcystine (NAC) (61mM). We found that NAC markedly decreased the G' at both 2 minutes and 12 minute

[figure not shown]

Figure 4. A. Sputum in asthma has an increased elastic modulus (G'). B. The G' of asthma sputum is significantly and inversely related to FEV1 (*ex vivo* data from 40 asthmatics and 11 healthy participants [red dots])

time-points after the addition of NAC (Fig 4A & B). This indicates that disulfide bonds are a mechanism of high sputum elasticity and a target for mucolysis in asthma, and it suggests thiol-based compounds as a rational mucolytic strategy.

2 STUDY RATIONALE

Because we have shown that the high elasticity of asthmatic mucus can be markedly decreased with NAC ex vivo (Fig 4), we propose here an *in vivo* study to treat asthmatics with NAC to improve their lung function. It is perhaps surprising that inhaled NAC has not been tested in a clinical trial in asthma, but a significant reason has been the uncertainty outlined above for the role of mucus in chronic disease. Another factor has been that clinical trials of NAC in COPD and cystic fibrosis have had not been consistently encouraging. However, these trials have not had a biomarker to select patients who might benefit and they have used orally administered NAC, which does not achieve detectable drug concentration in airway lining fluid⁶. Our proposal to test the efficacy of NAC in a specific patient subgroup identified by a biomarker (CT imaging) is timely and addresses a novel approach to asthma treatment. Although NAC is a suboptimal mucolytic, we are confident that high dose (20%) treatment will effectively lyse airway mucus to improve airflow and pave the way for later clinical trials of a thiol-saccharide.

2.1 Risk / Benefit Assessment

Inhaled NAC carries a relatively low risk profile. The main side effects from inhalational use are nausea, reported in 2-7% of cases, and vomiting, reported in 9-12% of cases. Other reported side effects without documented incidence rates include stomatitis, cough, hemoptysis, rhinorrhea, fever, and chills. Rarely, NAC has been associated with increased intracranial pressure and somnolence. Although these later side effects have been documented in the medical literature, our team of physicians, experienced in using NAC clinically, has not encountered these more serious side effects.

Mucus impaction and the concomitant airway obstruction are associated with severe activity limitation and disease-associated impairment. Currently, there are few effective

mucolytics utilized as part of standard clinical care of patients with severe asthma. This is due in part to the lack of clinical trial data on the effectiveness of NAC, the only nebulized mucolytic currently indicated for asthma. Our preliminary data, utilizing CT imaging and a novel scoring system, can identify and target a subgroup of patients who may benefit from inhaled mucolytic treatment more so than the asthmatic population as a whole.

To minimize risk, our study team of experienced clinicians will supervise the initial administrations of the study drug in a controlled environment located within a hospital setting.

3 STUDY OBJECTIVES

3.1 Primary Objective

The primary objective is to assess the clinical efficacy as measured by the change in pulmonary function over the seven day treatment period.

3.2 Secondary Objectives

The secondary objectives are to assess the clinical efficacy as measured in a subgroup of participants by the change in CT mucus score from baseline to end of treatment, and identify characteristics of those participants who benefit from mucolytic treatment.

4 STUDY DESIGN

4.1 Study Overview

This is a single center, double-blind, randomized, 2 period crossover trial. We propose a sample size of 30. Following a five-day run-in period, during which participants will self-administer 0.9% normal saline by nebulizer three times per day, each participant will be randomized to receive a nebulized dose of study drug three times per day for seven days of either 20% NAC (active) or 0.9% saline (placebo). Following a 28-day washout period, participants will be switched to the alternate group for 7 days of treatment. Participants will be assigned to the treatments in random order. Evaluations will be taken at baseline, end of run-in, start of second treatment period, and at the end of each 7-day treatment period.

Screening data will be reviewed to determine participant eligibility. Participants who meet all inclusion criteria and none of the exclusion criteria will be entered into the study.

The following treatment regimens will be used:

- Experimental treatment of NAC 20%
- Placebo treatment of 0.9% saline

Total duration of participation will be nine weeks. Total duration of the study is expected to be 2 years.

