9.3 Visit 3 (Day 0)

- 1. Record changes to concomitant medications.
- 2. Perform abbreviated physical examination.
- 3. Perform and record vital signs.
- 4. Perform and record oximetry.
- 5. Perform and record urine pregnancy test.
- 6. Perform and record spirometry.
- 7. Perform and record post-bronchodilator spirometry.
- 8. Provide education on use of personal nebulizer and administration of study medication.
- 9. Dispense study drug and initiate study diary.
- 10. Perform RN/MD supervised administration of first run-in dose of nebulized 0.9% normal saline.
- 11. Schedule participant for Visit 4 in 5 days.

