9.4 Visit 4 (Day 5)

- 1. Record any adverse experiences and/or review participant diary for adverse experiences and exclusionary medication use.
- 2. Record changes to concomitant medications.
- 3. Perform abbreviated physical examination.
- 4. Perform and record vital signs.
- 5. Perform and record oximetry.
- 6. Perform and record urine pregnancy test.
- 7. Perform and record spirometry.
- 8. Perform and record post-bronchodilator spirometry.
- 9. Collect any unused study drug.
- 10. Review diary card.
- 11. Randomize if adherence is greater than or equal to 80% during run-in.
- 12. Provide education on use of personal nebulizer and administration of study medication.
- 13. Dispense study drug and initiate study diary.
- 14. Perform RN/MD supervised administration of first dose of nebulized study drug.
- 15. Schedule participant for Visit 5 in 7 days.

Version #:1.5 Version Date: 8/5/2016 Page 27 of 41

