12.4 Replacement of Participants

Participants who withdraw from the study treatment will be replaced.

Participants who withdraw from the study will be replaced.

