14.3 Analysis of Primary Endpoint

The primary outcome is the % change in FEV1 from the start to the end of the treatment period (either placebo or 20% NAC). The first analysis will be to test the assumption of negligible carryover effects from study period 1 to period 2. We will compare the sum of the outcome values measured in the two periods for each participant across the 2 sequence groups (placebo-20% vs. 20%-placebo) using an unpaired t-test. After no or negligible carryover effect has been confirmed, we will test for the difference in treatment effects between placebo and 20% NAC using a paired t-test.

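### The saline run-in precedes period 1 only, and the primary paired t-test has no period term to absorb a period effect if that difference changes FEV1

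*Combined protocol and SAP*

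**What the plan says.** Section 4.1 describes the design: "This is a single center, double-blind, randomized, 2 period crossover trial". The run-in comes before randomisation: "Following a five-day run-in period, during which participants will self-administer 0.9% normal saline by nebulizer three times per day". It starts at Visit 3, where 9.3 lists: "Perform RN/MD supervised administration of first run-in dose of nebulized 0.9% normal saline". Entry to period 1 at Visit 4 depends on it: "Randomize if adherence is greater than or equal to 80% during run-in", which is at least 12 of 15 doses (5 days × 3).

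For the second period, 4.1 says: "Following a 28-day washout period, participants will be switched to the alternate group for 7 days of treatment". Visit 6 (9.6), midway through the washout, dispenses nothing, and Visit 7 (9.7) goes straight to study drug.

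The measurement times are listed in 4.1: "Evaluations will be taken at baseline, end of run-in, start of second treatment period, and at the end of each 7-day treatment period". The primary outcome (14.3 and the synopsis) is the percentage change in FEV1 from the start to the end of each treatment period. The analysis begins with a carryover check, an unpaired t-test on each participant's sum over the two periods, compared between sequences. Then: "we will test for the difference in treatment effects between placebo and 20% NAC using a paired t-test". No period term, period test or period-adjusted estimate is given.

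Allocation is 1:1 from a computer-generated scheme (7.1), with blocking neither stated nor excluded. Section 12.4 adds: "Participants who withdraw from the study will be replaced". It does not say which sequence a replacement receives.

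**The concern.** The outcome is a change from a starting value, and the two starting values are taken under different conditions. Suppose that beginning thrice-daily nebulised saline moves FEV1. Part of that movement has already happened by the period 1 starting value, but all of it falls inside the period 2 change. Saline is the placebo, and NAC is also given as a nebulised solution, so the same could apply under both treatments. The result would be a period effect. Section 14.4 plans to examine the FEV1 change over seven days of saline, so the plan itself allows that there may be one.

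A paired t-test of NAC minus saline pools the two sequences. A period effect enters with opposite signs in the two sequences. It therefore adds to the error variance and, if the sequences are unequal in size, to the estimate. What is at stake is some power, and the accuracy of the single reported NAC effect.

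**Working it through.** **Inputs.** From 14.6: SD 19, two-sided alpha 0.05, effect 10, N = 30, power 80%. From 14.3: paired t-test. Assumed, because the documents give no value: the period difference P (mean change in period 2 minus period 1 on the same treatment), taken as 0 to 10 points. Also assumed: 19 is the SD of the paired NAC-minus-saline difference. Section 14.6 describes it as the SD of a single 7-day change; the two are equal only if the correlation between periods is 0.5.

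**The plan's own figure.** n = (19 × (1.960 + 0.842) / 10)² = 28.3, so 29. With the t distribution, n = 31, and power at N = 30 is 79.6%. The stated 30 and 80% reproduce on this reading.

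**Where P goes.** Let τ be the NAC effect, n1 the number taking NAC first and n2 the number taking saline first. The mean NAC-minus-saline difference is
- NAC first: τ − P
- saline first: τ + P

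The paired mean therefore estimates τ + P(n2 − n1)/30. With equal sequences the bias is zero and the SD is about √(19² + P²).

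**Why the carryover check does not help.** With m the mean period 1 change on saline, the expected sum is (m + τ) + (m + P) for NAC first and m + (m + P + τ) for saline first. Both equal 2m + τ + P, so P cancels from the comparison. The check can neither detect nor remove it.

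**Equal sequences, 15:15 (simulated, at least 100,000 trials per case).**

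| P (assumed) | SD of paired difference | Paired test: power | Paired test: type I error | Period-adjusted: power |
|---|---|---|---|---|
| 0 | 19.0 | about 80% | 5.0% | 79.5% |
| 5 | √(361 + 25) = 19.6 | about 78% | about 4.4% | 79.5% |
| 10 | √(361 + 100) = 21.5 | 71% | about 2.8% | 79.5% |

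**Unequal sequences.** At 18:12 the shift is P × 6/30 = 0.2P, that is 1 point at P = 5 and 2 points at P = 10.
- NAC-first larger: the estimate of 10 becomes 9 or 8, and paired power is about 68% or 51%.
- Saline-first larger: the estimate becomes 11 or 12, and nominal power rises.
- Period-adjusted test: the estimate stays at 10, with power about 78%.

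**How likely is such a split?** If allocation were simple (an assumption), the Binomial(30, 0.5) probability of 18:12 or worse is 36%. A blocked list would make it less likely.

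**Cost of adjusting when P = 0.** The standard error of the adjusted estimate is (19/2) × √(1/n1 + 1/n2) on 28 degrees of freedom.
- 15:15: 3.47, power 79.5% against 79.6% for the paired test
- 18:12: 3.54, power 77.8%
- 20:10: 3.68, power 74.7%

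The losses are about 0.1, 2 and 5 points.

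**The case against.** A reader might infer that the two periods start from different FEV1 levels by design, and that the primary estimate is therefore biased and the trial loses power. The documents do not support that. Only the condition before each period differs by design; whether mean FEV1 differs depends on a saline effect that is never quantified. At P = 0 the paired test is marginally the better one. A P of 10 would mean that the run-in difference alone moves FEV1 by as much as the NAC effect the trial is powered to find. Up to 5 points, the cost at 15:15 is about 2 points of power.

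Nor is the test's validity threatened by chance imbalance. At 15:15 it is conservative. Averaged over unrestricted 1:1 allocation, its type I error stays at about 5% for P of 5 or 10, and the bias averages to zero. Withdrawal or replacement related to sequence could produce a systematic bias, but no such mechanism or rate is documented. A blocked list, or replacement into the same sequence, would fit the text equally well.

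It is also tempting to add pre-dose albuterol to the run-in effect. Section 7.4.1 ties that albuterol to the treatment periods; its use during run-in can only be inferred from the general diary instructions in Appendix A. The point does not need it.

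Finally, section 14 promises a detailed SAP that may modify the analysis. That leaves room for the change, but the documents state none. The 36% probability is thus an assumption and the bias is conditional. It still stands that one trial yields one split and one estimate, and that the stated analysis has no protection against a period effect.

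**Conclusion.** The point holds in conditional form and is a cheap improvement, not a flaw that invalidates the primary test. The documents establish that the run-in precedes period 1 only, that the paired t-test has no period term, and that the carryover check cannot stand in for one. Everything about size is conditional. Over an assumed period difference of 0 to 10 points, the power loss at 15:15 runs from nothing to about 8 points, and the shift at 18:12 is up to 2 points in either direction, set against a target effect of 10. These figures rest on SD 19 applying to the paired difference and on all 30 participants contributing both periods.

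**What to change.** In 14.3 and the synopsis, replace the paired t-test with the period-adjusted crossover analysis. For each participant take period 1 minus period 2, compare these differences between the two sequences with a two-sample t-test, and halve the difference in means to obtain the NAC effect. The expected values are τ − P for NAC first and −τ − P for saline first, so P cancels and half the difference is τ. A mixed model with treatment and period is equivalent. Report the estimated period effect alongside the NAC effect.

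The adjustment assumes that the saline effect is additive and similar under both treatments; if it is not, adjusting for period does not fully remove it.

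The cost is one degree of freedom and, when there is no period effect, the small power losses shown in the working (about 0.1 point at 15:15, 2 at 18:12, 5 at 20:10). No visit, dose or measurement changes.
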